## Baseline characteristics

Baseline characteristics (those that are ascertained at enrollment [admission into wasting treatment], before the treatment is administered) will be presented by treatment group and by wasting severity status. These characteristics will be assessed with descriptive statistics (means and standard deviations for continuous variables, and proportions for categorical variables). Baseline characteristics (sex, age and anthropometry at admission, caregiver-reported morbidities at admission, presence of morbidity as per health worker documentation [failed appetite test, fever (temperature  $\geq 38^{\circ}\text{C}$ ), high respiratory rates (50 breaths per minute for children up to 12 months or age; 40 breaths per minute for children 12 to 59 months), anemia and severe anemia (defined as above), skin condition, dehydration, oral candidiasis) will be adjusted for in the analyses if it is both (i) associated with treatment outcomes or relapse in published literature, and (ii) imbalanced between treatment arms defined as a difference of at least 5% in absolute terms.

A shell table depicting the baseline information that will be available, and presented by treatment group, is presented in Table 6.

Table 6. Baseline characteristics that will be collected at study enrollment and presented by treatment group

		SMS-RUTF		S-RUTF		Control	
		MAM N=	SAM N=	MAM N=	SAM N=	MAM N=	SAM N=
	Child/caregiver characteristics						
	Age at admission, mo (SD)						
	Male sex, %						
	Wasting episode characteristics						
	WLZ at admission (SD)						
	WLZ < -2, %						
	MUAC at admission, mm (SD)						
	MUAC < 125 mm, %						
	Edema present, %						
	Type of admission						
	New case, %						
	Readmission, %						
	Relapse, %						
	Anemic, %						
	Hemoglobin, g/dL (SD)						

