All analyses will be delineated in detail in the trial Statistical Analysis Plan (SAP) which will be developed and finalized prior to initiation of enrollment. A summary is given here.

The study is powered for separate comparisons between (i) the control group and SMS-RUTF, and (ii) between the control group and S-RUTF. All analyses will be stratified by MAM vs SAM status.

Baseline characteristics will be assessed with descriptive statistics (means and standard deviations for continuous variables, and proportions for categorical variables). Baseline characteristics will be adjusted for in the analyses if it is both (i) associated with treatment outcomes or relapse in published literature and (ii) imbalanced between treatment arms as determined by statistically significant t-test or χ^2 tests with 5% significance level.

For binary outcomes, we will use log-binomial regression to estimate relative risks (RRs) and 95% confidence intervals (CIs) for the RRs, adjusting for any baseline factors as appropriate. Non-inferiority will be declared if the lower bound of a one-sided 95% CI for the RR lies entirely below the non-inferiority margin of a relative 12.5%. For continuous outcomes, we will use linear regression to estimate differences in that outcome between treatment arms, adjusting for any baseline factors as appropriate. For superiority analyses (relapse), we will use a two-sided 95% CI and superiority will be declared if the lower bound of the 95% CI for the relative risk is above 1.0.

Non-inferiority analyses can be spuriously favored by ITT analyses because non-compliance diminishes any treatment effects, thus biasing the effect size toward the null (35). We will therefore repeat all non-inferiority analyses with a per-protocol (PP) population, restricting the analyses to only children who comply with their full treatment course, per caregiver report. The ITT and PP results will be presented side-by-side for non-inferiority analyses; superiority analyses will be analyzed as ITT only.

Adverse event (AE) and serious adverse event (SAE) monitoring and reporting

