## Statistical methods

We will conduct two separate comparisons between (i) the control group and SMS-RUTF, and (ii) between the control group and S-RUTF. All analyses will be done separately by wasting severity status (MAM vs SAM); that is, all analyses will be conducted and presented among MAM children and among SAM children separately. No adjustments for multiple comparisons will be made.

For binary outcomes, we will use log-binomial regression to estimate relative risks (RRs) and 95% confidence intervals (CIs) for the RRs, adjusting for any baseline factors as appropriate (described further below). If the regression model is adjusted, we will present both crude (unadjusted) and adjusted model results. If the models do not converge, we will use Poisson regression models with robust estimation of standard errors (26) and report which model was used. Non-inferiority will be declared if the lower bound of a one-sided 95% CI for the RR lies entirely below the non-inferiority margin of a relative 12.5%. For superiority analyses, we will use a two-sided 95% CI and superiority will be declared if the lower bound of the 95% CI for the relative risk is above 1.0. All analyses will be adjusted for health center to reflect the stratified randomization (27–29).

For continuous outcomes measured at one timepoint, we will use linear regression to estimate differences in that outcome between treatment arms, adjusting for any baseline factors as appropriate and health center (as explained above). Both unadjusted and adjusted model results will be presented.

For any outcome for which non-inferiority is demonstrated, we will then sequentially test for superiority. In these cases, we will report both non-inferiority and superiority results. The superiority analysis will be considered exploratory, as the study power calculations were based on non-inferiority effect size.

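### Covariate adjustment depends on a chance-driven imbalance rule with no defined scale for means, no model is named as deciding, and continuous primary outcomes need not be adjusted for their own admission value

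*SAP*

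**What the plan says.** The SAP, Baseline characteristics, sets two conditions that must both hold before a baseline characteristic enters a model. It must be "associated with treatment outcomes or relapse in published literature", and it must be "imbalanced between treatment arms defined as a difference of at least 5% in absolute terms". The candidates are "sex, age and anthropometry at admission, caregiver-reported morbidities at admission, presence of morbidity as per health worker documentation"; the morbidity list that follows includes anemia and severe anemia. The same section summarises continuous variables as means and SDs. It does not say how 5% applies to a mean, or which pair of the three arms is compared. The Analysis frame section carries the same rule into the CACE analysis.

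The Protocol, Statistical analysis, keeps the literature condition but uses another trigger: the characteristic must be "imbalanced between treatment arms as determined by statistically significant t-test" or the corresponding χ² test at the 5% level.

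For the models themselves, the SAP, Statistical methods, has continuous single-timepoint outcomes analysed by linear regression, "adjusting for any baseline factors as appropriate and health center". Health center is therefore always in the model and other baseline factors are conditional. For binary outcomes, if the model is adjusted, "we will present both crude (unadjusted) and adjusted model results". For continuous outcomes both versions are always shown. No sentence says which one decides non-inferiority or superiority.

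SAP Tables 1 and 4 rank anthropometry (WLZ/WHZ, MUAC, weight, height/length, LAZ/HAZ, WAZ) and hemoglobin, each at discharge and at 3 months, as primary. Admission anthropometry and hemoglobin are collected (Protocol, Anthropometric and clinical procedures).

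**The concern.** There are three separate weaknesses.

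- **The trigger cannot be applied as written to variables reported as means.** Whoever runs the analysis must choose a scale, and the scale, not prognostic value, then settles what enters. The covariate set can differ across the four analyses (two product comparisons in each of two severity strata).
- **Two results can exist for one outcome with no rule for choosing between them.** If they fall on opposite sides of a margin, the SAP does not say which counts.
- **The admission value of a continuous outcome is not required in its model.** It is a natural covariate, measured before treatment. For hemoglobin the gap is wider: only anemia and severe anemia are candidates, so the continuous admission value would stay out even if the arms differed on it.

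What is at stake is precision on continuous primary outcomes and a single pre-specified answer for every outcome.

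**Working it through.** **Inputs.** From the documents: 360 enrolled per arm and stratum; 306 analysed after 15% attrition; 236 recovered (Protocol, Table 4); 80% power with two-sided α = 0.05 for superiority and one-sided 0.05 for non-inferiority; hemoglobin SD 13 (MAM) and 11.2 g/L (SAM); detectable differences from SAP Table 4. Assumed: the correlation r between admission and follow-up values, shown from 0.3 to 0.9.

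**1. The plan's own figure.** The unadjusted detectable difference is (1.960 + 0.842) × SD × √(2/n).
- MAM hemoglobin, n = 306: 2.802 × 13 × √(2/306) = 2.94 g/L (SAP: 2.9).
- SAM hemoglobin, n = 236: 2.802 × 11.2 × √(2/236) = 2.89 g/L (SAP: 2.9).

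Both reproduce with no correlation term, so Table 4 assumes no gain from the admission value. They reproduce only with different n: SAM at 306 gives 2.54 and MAM at 236 gives 3.35. Table 4 should state its n.

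**2. How often the trigger fires by chance, 360 per arm, one pair of arms.**

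Read as 5 percentage points for a binary covariate with prevalence p, SE = √(2p(1−p)/360):

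| p | SE | 0.05/SE | P(trigger) |
|---|---|---|---|
| 50% | 0.0373 | 1.34 | 18% |
| 20% | 0.0298 | 1.68 | 9% |
| 10% | 0.0224 | 2.24 | 2.5% |

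Read as 5% of the mean for a continuous covariate, I used Table 4 means and SDs back-calculated from its detectable differences as stand-ins for admission values, with MUAC taken in mm as in the discharge row. Example, MAM WLZ at n = 306: SD = 0.26/(2.802 × √(2/306)) = 1.15; threshold 0.05 × 1.52 = 0.076; SE = 1.15 × √(2/360) = 0.086; P = 37%. Across both strata and n = 236 or 306, P is about 0% for MUAC and height, 0.05–4% for weight, and 22–47% for WLZ, HAZ and WAZ. The same rule almost never admits MUAC and often admits z-scores, for reasons of scale alone.

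**3. Precision from the admission value.** With ANCOVA the SE is multiplied by √(1−r²):

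| r | SE factor | SE falls by | MAM hemoglobin, 2.94 g/L becomes | MAM height, 1.87 cm becomes |
|---|---|---|---|---|
| 0.3 | 0.954 | 5% | 2.81 | 1.78 |
| 0.5 | 0.866 | 13% | 2.55 | 1.62 |
| 0.7 | 0.714 | 29% | 2.10 | 1.34 |
| 0.9 | 0.436 | 56% | 1.28 | 0.82 |

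Table 4 gives no SD for height, so 1.87 cm is taken as stated.

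**4. Recovery.** Control rate 76%, relative margin 12.5% (9.5 points), 306 per arm. Unadjusted SE = √(2 × 0.76 × 0.24/306) = 0.0345; power = Φ(0.095/0.0345 − 1.645) = 86.6%. If covariates explain 5–15% of outcome variance (assumed), power is 88.1–91.0%. On the log-RR scale, 90.2% becomes 91.5–93.9%. In simulation, the SE of the log RR fell by at most 1%, by 2% and by 6% for a covariate with odds ratio 1.35, 1.82 and 2.72 per SD.

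**The case against.** The strongest reply is that validity is not in question. Under randomisation, omitting a prognostic covariate costs precision and does not bias the comparison, and in a non-inferiority test a wider interval makes the claim harder to reach. The 18% is a rate of adjusting, not a false-positive rate. A reader might infer that the rule inflates type I error; nothing in the documents or in the arithmetic above shows that. This part of the reply stands.

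A reader might also infer that the plan certainly discards much of its precision. The documents do not support this as a fact, because they give no correlation. At r = 0.3 the SE falls by only 5%. Analyses are run within MAM and within SAM, so the entry cut-offs narrow admission MUAC and WLZ, although only partly because either criterion suffices. Discharge on reaching a threshold compresses discharge values. Both may lower r for MUAC and WLZ. Height at r = 0.9 is the favourable end of the range. Recovery and relapse, which the SAP calls its key objectives, and length of stay have no admission value; weight gain is already a change from admission.

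Other mitigating points are fair: health center is always in the model, a literature condition also applies, the 5% rule is clear for the percentage rows of SAP Table 6, 5% of the mean is a possible reading for the others, and treatment codes stay concealed until the analysis is finished. The Protocol section describes itself as a summary and defers to the SAP, so the conflicting trigger is a point to tidy.

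None of this gives the trigger a defined scale, names a deciding model, or brings admission hemoglobin into the candidate list.

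**Conclusion.** The point holds in three parts. The imbalance rule makes the covariate set depend on chance and measurement scale. No model is designated as deciding. Continuous primary outcomes are not required to be adjusted for their admission values, and continuous admission hemoglobin is excluded altogether.

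The size is conditional. For continuous outcomes with an admission value, the forgone reduction in SE runs from about 5% (r = 0.3) to 56% (r = 0.9), and r is an assumption throughout. For recovery the gain is small, and for binary outcomes generally the argument rests on pre-specification. This should be changed because the improvement is free; it is not a flaw that invalidates the trial.

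**What to change.** In the SAP, Baseline characteristics, delete the imbalance condition and replace it with covariate sets that apply whatever the observed balance:

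- **Continuous outcomes with an admission value** (WLZ/WHZ, MUAC, weight, height/length, LAZ/HAZ, WAZ, hemoglobin): that admission value, age, sex and health center. Add continuous admission hemoglobin explicitly.
- **Common binary outcomes** (recovery, and relapse where events allow): admission MUAC, admission WLZ/WHZ, age, sex and health center.
- **Rare binary outcomes:** a reduced set, stated in advance. At the lowest relapse figure in Table 4 (6.8%) and 236 per arm, one comparison has about 2 × 236 × 0.068 = 32 events, too few for four covariates plus 30 centers. The Poisson fallback in Statistical methods covers non-convergence only.

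In Statistical methods, name this model as the one on which non-inferiority or superiority is decided, and report the unadjusted result as supportive. Apply the same sets in the CACE analysis, and align the Protocol's Statistical analysis summary.

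The cost is wording only: every variable listed is already collected, and no change to sample size or procedures is needed. The new text should be dated and settled before treatment codes are released.

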#### Interim analyses and data monitoring

No interim analyses will be done. Adverse events (AEs) and severe adverse events (SAEs) will be evaluated at every follow up visit during treatment (weekly for children with SAM and bi-weekly for children with MAM), and will be addressed and reported as per the study Standard Operating Procedures (SOPs).

A Data Safety and Monitoring Board (DSMB) will be convened prior to enrollment, who will monitor study progress and participant safety (including adverse events monitoring). Data reports will be prepared for the DSMB reporting the following:

- Study accrual profile and recruitment numbers by month
- Baseline characteristics
- Protocol violations
- Recovery and relapse rates
- Treatment outcomes
- (Serious) adverse events

The above data will be pooled across sites, blinded, and stratified by MAM vs SAM. All data will retain blinding at all times. No closed session (unblinded) reports will be done. No statistical testing will be done on any data reported to the DSMB; only descriptive data will be reported. A shell table depicting the outcome and adverse event summaries that will be sent to the DSMB for monitoring is depicted in Table 7. These monitoring reports will be sent to the DSMB prior to the DSMB meetings. The DSMB will meet after approximately 300 SAM children have treatment outcomes, or at the call of the DSMB chair or study investigators.

Table 7. Shell table of outcome and safety data to be monitored by DSMB

		MAM			SAM		
		Arm 1	Arm 2	Arm 3	Arm 1	Arm 2	Arm 3
Treatment outcomes							
		N with outcome data available =	N with outcome data available =	N with outcome data available =	N with outcome data available =	N with outcome data available =	N with outcome data available =
Recovered from treatment							
Death							
Default							
Non-response							
Referral							
Transfer							
Post-discharge outcomes							
		N with $\geq 1$ post-discharge visit =	N with $\geq 1$ post-discharge visit =	N with $\geq 1$ - post-discharge visit =	N with $\geq 1$ post-discharge visit =	N with $\geq 1$ post-discharge visit =	N with $\geq 1$ post-discharge visit =
		N of follow up visits =	N of follow up visits =	N of follow up visits =	N of follow up visits =	N of follow up visits =	N of follow up visits =
Relapse within 3 months							
Adverse event data*							
		N with $\geq 1$ follow up visit completed =	N with $\geq 1$ follow up visit completed =	N with $\geq 1$ follow up visit completed =	N with $\geq 1$ follow up visit completed =	N with $\geq 1$ follow up visit completed =	N with $\geq 1$ follow up visit completed =
		N of visits completed:	N of visits completed:	N of visits completed =	N of visits completed:	N of visits completed:	N of visits completed:
	Anemia						

Adverse event (as per documentation by health center staff)	Severe anemia						
	Failed appetite test**						
	Fever**						
	Dehydration**						
	Skin condition**						
	Oral candidiasis**						
Serious adverse event (death or hospitalization***)	Death						
	Referral to inpatient care						
	Transfer to inpatient care						
Classification of serious adverse events (relatedness to intervention)	Unclassifiable or not assessable						
	Conditional or not classified						
	Improbable						
	Possible						
	Probable or plausible						
	Certain						

\*Adverse event rates are reported as number of children with the event, divided by number of children with data available. For example, anemia rate is the number of children with anemia at least one follow up visit, divided by the number of children who had at least one follow up visit.

\*\*Not recorded in the medical records for MAM children

\*\*\*Including referral or transfer to inpatient care for wasting.

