AEs and SAEs will be closely monitored and addressed in both study arms through the routine monitoring of children under wasting treatment, through weekly in-facility visits for SAM children and bi-weekly for MAM, as per national guidelines. AEs/SAEs will be documented in detail and reported to the study leadership. We will ensure the child receives appropriate medical care and monitoring as per guidelines. Definitions of AEs and SAEs are delineated in the annexed SOP (see Annex 4), where procedures are also documented in further detail.

A Data Safety and Monitoring Committee (DSMC) will be formed prior to initiation of enrollment to monitor SAEs, to review the protocol, and evaluate the statistical analysis plan. The DSMC will consist of a professor in pediatrics with experience in child wasting, a professor in epidemiology, and a statistical analysis expert. Monthly AE/SAE summaries will be compiled and sent to the chair of the DSMC. In case of a disproportional rise in monthly SAEs, the chair will convene the DSMC to decide whether the trial should be halted. Given the short character of the trial, there will be no interim analysis.

Early withdrawal from the study

While the study team intends to follow all participants from admission to treatment until 3 months post-discharge from treatment, participants have the option to withdraw from the study at any time for any reason, in accordance with the principles of voluntary participation (outlined in more detail in the section on Ethics below). A participant may be withdrawn from the study by the principal investigator (who will be blinded to treatment allocation) if they believe it is in the participant's best interest to do so. The reason for early withdrawal will be documented in the participant's study file, and if the withdrawal is due to an SAE, prompt medical treatment will be ensured.

Ethics

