### Controls

#### Blinding

This study will be triple blinded; that is, the study investigators, participants, and outcome data collectors will be blinded to randomization assignment. The study products will have identical packaging, and will be stored in boxes that are identically labeled to the extent possible. The products will be identified only with one of three alphabet letters, and the codes to these alphabet letters will not be accessible by the study team until after analyses are completed. While the participants will technically be blinded to their treatment assignment, the products will likely differ in their taste and appearance, meaning that true blinding for participants may not be possible due to the nature of their different recipes. However, we expect concerns of bias due to this to be minimal.

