#### Method of treatment assignment/randomization

A statistician who is not part of the research team will generate a randomization scheme for the allocation of the 3 supplements. Each unique randomization number is randomly allocated to 1 of 9 letter codes (e.g., A, E, I, Z, K, T, N, E, S)—3 letters for the SMS-RUTF supplement, 3 letters for the S-RUTF supplement and 3 letters for the standard RUTF (control group)—using a computer program in blocks of 45. Without the investigators' knowledge, the producers will be informed which letters to print on the package of each supplement. Information regarding the assignment of the letter codes to the intervention and control supplements will be stored electronically by the director of Nutrition, Diets and Health unit of IFPRI, inaccessible by the investigators, until analysis is completed.

Eligible children will be randomly assigned to one of the three study groups at study inclusion. The study staff will open the sealed envelope corresponding to the next sequential participant identification number in the presence of an eligible mother-child pair (in order of arrival) and will provide them with the RUTF supplement according to the letter code. The participant's number, as well as the letter code, will be recorded on the study participant's card, their medical records, and scanned into the electronic data capture system.

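### The DSMB sees outcomes and SAEs by masked arm and may be asked to decide on halting, but the supplied plan gives it no way to learn which arm is the control

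*SAP*

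**What the plan says.** **Monitoring rule.** SAP, Interim analyses and data monitoring: "The above data will be pooled across sites, blinded, and stratified by MAM vs SAM". The section continues: "All data will retain blinding at all times. No closed session (unblinded) reports will be done". It adds: "No statistical testing will be done on any data reported to the DSMB; only descriptive data will be reported". The DSMB meets once about 300 SAM children have treatment outcomes, or when its chair or the investigators call a meeting.

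**What the DSMB receives.** SAP Table 7, titled "Shell table of outcome and safety data to be monitored by DSMB", has columns Arm 1, Arm 2 and Arm 3 within MAM and within SAM. Its rows include recovery, death, default, non-response, relapse, adverse events, SAEs and relatedness to the intervention. No column is marked as control.

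**What the committee is asked to do.** Protocol, section on AE and SAE monitoring and reporting: after a disproportional monthly rise in SAEs, "the chair will convene the DSMC to decide whether the trial should be halted". The same section refers to Annex 4 for more detailed procedures.

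**Who may see the code.** SAP, Method of treatment assignment/randomization: the key is held electronically by a unit director at IFPRI, "inaccessible by the investigators, until analysis is completed". SAP, Blinding, withholds it from the study team until the analyses are finished. Protocol, Randomization procedure, has the envelope locked away until the analysis is done and states no exception.

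**How many codes.** SAP, Method of treatment assignment/randomization: "Each unique randomization number is randomly allocated to 1 of 9 letter codes", three letters per product; the Protocol agrees. SAP, Blinding: "The products will be identified only with one of three alphabet letters".

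**The concern.** A committee that may be asked to halt a trial should be able to interpret the data it is shown. If one masked column has more deaths or inpatient transfers than the other two, a new product may be doing harm, or the standard product may be doing worse than both new ones. These are different findings, and they bear differently on children still in treatment and on what the sponsor is told. The same ambiguity arises when one column looks better than the other two. Because the SAP's blinding rule is absolute, a DSMB that asked for the arm identities would be asking for something the SAP excludes.

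A lesser question is how Table 7 gets filled. If the products carry nine letters, someone must say which three belong together, and the SAP does not say who.

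**Working it through.** The plan states no figure on this point, so there is nothing to reproduce. The check sets the texts side by side and adds simple counts.

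**1. What masked columns can show.** Three products can be assigned to three columns in 3! = 6 ways. A given column is the control in 2! = 2 of these, so 2/6 = 1/3. This is the position before any other information is used. Table 7 can reveal a difference between arms; it cannot show which product is behind it.

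**2. Is there a route to arm identity?**

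| Text | Who is kept from the code | Release to the DSMB? |
|---|---|---|
| SAP, Blinding | study team | not mentioned |
| SAP, Method of treatment assignment/randomization | investigators | not mentioned |
| Protocol, Randomization procedure | general lock, no exception stated | not mentioned |
| SAP, Interim analyses and data monitoring | all data blinded at all times | unblinded reports ruled out |

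None of the four provides a route, and the fourth rules out unblinded reports. Yet the key is within reach of people outside the study team: a unit director holds it, a statistician outside the research team generates the scheme, and the producers are told which letters go on which product.

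**3. Why the grouping step matters.** Nine codes over three arms is 9/3 = 3 codes per arm. At the planned meeting, with equal allocation:

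- per arm: 300/3 = 100 SAM children
- per code: 300/9 = about 33 SAM children

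As an illustration, take the 20.1% SAM transfer rate in SAP Table 4. The 95% half-width for a difference between two groups of size n is 1.96 × √(2 × 0.201 × 0.799 / n).

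- n = 100: 1.96 × √0.003212 = 0.111, or 11.1 points
- n = 33.3: 1.96 × √0.009636 = 0.192, or 19.2 points

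Expected transfers are 100 × 0.201 = 20.1 per arm and 33.3 × 0.201 = 6.7 per code. Someone without the key cannot work out the grouping, because nine letters split into three unlabelled sets of three in 9!/((3!)³ × 3!) = 280 ways. A partial key, saying which letters go together, is enough for Table 7 and identifies no product.

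**The case against.** **Masked review is a legitimate choice.** Table 7 is split by arm, so an outlying arm is visible. The decision the Protocol describes concerns the whole trial and can be taken without naming the arm, and the chair can call a meeting at any time. All of this stands. A reader might infer that the committee cannot act on a harm signal, but the documents do not support that. What remains is that it would act without knowing whether the outlying arm is a new product or the control.

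**Who is barred.** A reader might infer that nobody may break the code before analysis. The SAP bars the investigators and the study team only; just the Protocol's envelope sentence reads as a general lock. That helps the fix, since an independent code holder already exists.

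**Closed sessions.** A reader might infer that the DSMB may not meet in private, or that by-arm results will circulate among staff. The SAP rules out unblinded reports, not private meetings, and says the reports go to the DSMB. It describes no wider circulation, though it does not restrict circulation either.

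**Computability.** A reader might infer that nine codes cannot be grouped, or that comparisons with control cannot be run under the key-release rule. Neither follows. A partial key fills Table 7, and masked pairwise contrasts can be estimated in both directions and labelled afterwards. If the three letters in the Blinding section are correct, no grouping is needed. The grouping and labelling steps are unstated, not impossible.

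**Missing annexes.** Annex 4 and the SOPs may contain unblinding procedures. Nothing can be said here about code-breaks for individual participants, and a DSMB route may also be written there. If so, it would conflict with the SAP's absolute wording and would still need reconciling.

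**Timing.** SAP, Statistical methods, describes in the past tense children enrolled near the end of the study whose product was switched. Enrolment therefore appears to be at or near its end, which limits the benefit within this trial.

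**Conclusion.** The point holds in a limited form. As the supplied documents stand, the DSMB can see that an arm differs but has no stated means of learning whether it is a new product or the standard RUTF, while the Protocol gives the committee a halting decision. This is more than missing detail, because the SAP excludes unblinded reports outright.

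The gap concerns safety oversight. It changes no sample size, power, error rate or endpoint. It should be corrected because the remedy is cheap, but its practical value in this trial depends on how many children remain in treatment or follow-up.

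The conclusion assumes that the Protocol's DSMC and the SAP's DSMB are the same body, and that the unsupplied annex and SOPs contain no route for the DSMB. The 1-in-3 is a count of labellings, not an estimate from data. The transfer-rate illustration rests on the SAP's literature figure.

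The conflict between three and nine letters is a genuine inconsistency but a minor one. The Protocol also says nine, which makes nine the likelier intention without settling it.

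**What to change.** Keep masked by-arm tables as the default. In the SAP section on interim analyses and data monitoring, replace the absolute rule with:

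> By-arm tables go only to the DSMB. On the chair's request, the code holder releases arm identities to the DSMB members only; investigators and study staff remain blinded.

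Add the matching exception to the Protocol's Randomization procedure. If Annex 4 or an SOP already gives such a route, cross-refer to it and remove the conflict.

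As secondary clean-up:

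- Use one code count throughout, reconciling the SAP's Blinding section with its randomization section and with the Protocol.
- State that the code holder or the outside statistician supplies the nine-to-three grouping, without naming products, for Table 7 and for the masked analysis.

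The cost is a few sentences in the SAP and Protocol. The code holder and the outside statistician are already in place. The downside is that a few independent people may learn the arms, and if enrolment has ended the gain is confined to the remaining treatment and follow-up.
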